2.2. SECONDARY OBJECTIVES

2.2.1. KEY SECONDARY OBJECTIVES

If galcanezumab is statistically superior to rimegepant on the primary objective, the key secondary objectives, defined in Table A, will be tested with adjustment for multiplicity according to the methodology specified in Section 7.4.

Table A: Key Secondary Objectives and Endpoints

Objectives	Endpoints
To compare galcanezumab with rimegepant with respect to monthly migraine headache days.	The overall mean change from baseline in the number of monthly migraine headache days across the 3-month double-blind treatment period.

Document: **CCI**

Author: **PPD**

Version Number:

3.0

Version Date:

19May2023

CCI

Objectives	Endpoints
To compare galcanezumab with rimegepant with respect to 75% response rate.	The percentage of participants with $\geq 75\%$ reduction from baseline in monthly migraine headache days across the 3-month double-blind treatment period.
To compare galcanezumab with rimegepant with respect to monthly migraine headache days at: 
  Month 3  Month 2  Month 1 	The mean change from baseline in the number of monthly migraine headache days at: 
  Month 3  Month 2  Month 1
To compare galcanezumab with rimegepant with respect to migraine headache days with acute (abortive) migraine treatment.	The overall mean change from baseline in the number of monthly migraine headache days requiring medication for the acute treatment of migraine or headache across the 3-month double-blind treatment period.
To compare galcanezumab with rimegepant with respect to change in functioning.	The mean change from baseline in the Role Function-Restrictive (RF-R) domain score of the Migraine-Specific Quality of Life Questionnaire version 2.1 (MSQ v2.1) at Month 3.
To compare galcanezumab with rimegepant with respect to 100% response rate.	The percentage of participants with 100% reduction from baseline in monthly migraine headache days across the 3-month double-blind treatment period.

2.2.2. OTHER SECONDARY OBJECTIVES

The other secondary objectives, defined in, Table B will be tested without multiplicity adjustment.

Table B: Other Secondary Objectives and Endpoints

Objectives	Endpoints
To compare galcanezumab with rimegepant with respect to changes in disability and health-related quality of life.	Changes from baseline to Month 3 on the following measures: 
 • MSQ v2.1 total score, and Role Function-Preventive (RF-P) and Emotional Function (EF) domain scores • MIDAS (Migraine Disability Assessment) total score

Document: **CCI**

Author: **PPD**

Version Number:

3.0

Version Date:

19May2023

CCI

Objectives	Endpoints
To describe the safety and tolerability of galcanezumab and rimegepant.	Analysis of: 
 • treatment-emergent adverse events (TEAEs) • serious adverse events (SAEs) • discontinuation due to adverse events (AEs) • discontinuation rates • vital signs • laboratory measures

2.3. EXPLORATORY OBJECTIVES

The tertiary/exploratory objectives are listed in Table C and Table D.

Table C: Tertiary/Exploratory Objectives and Endpoints

Objectives	Endpoints
To compare galcanezumab with rimegepant with respect to change in participant global impression of the severity of migraine.	Mean change from baseline in the Patient Global Impression of Severity (PGI-S) at Month 3.
To compare galcanezumab with rimegepant with respect to change in moderate to severe headache days.	The overall mean change from baseline in the number of monthly moderate to severe headache days across the 3-month double-blind treatment period.
To compare galcanezumab with rimegepant with respect to change in Total Pain Burden.	Mean change from baseline in the Monthly Total Pain Burden across the 3-month double-blind treatment period.

Table D: Additional Exploratory Objectives and Endpoints.

Objectives	Endpoints
To assess onset of action*	
To compare galcanezumab with rimegepant with respect to weekly migraine headache days by Week 4, Week 3, Week 2, and Week 1	Mean change from baseline in the number of weekly migraine headache days in the months that galcanezumab was superior to rimegepant

Document: **CCI**

Author: **PPD**

Version Number:

3.0

Version Date:

19May2023

CCI

To compare galcanezumab with rimegepant with respect to rimegepant with respect to 50% response rate at Month 3, Month 2, and Month 1	Percentage of participants with $\geq 50\%$ reduction from baseline in monthly migraine headache days at Month 3, Month 2, and Month 1
To compare galcanezumab with rimegepant with respect to 50% response rate at weeks 4, Week 3, Week 2, and Week 1	Percentage of participants with $\geq 50\%$ reduction in Weekly migraine headache days at weeks 4, 3, 2, 1 in the months that galcanezumab was superior to rimegepant
To assess sustained response	
To compare galcanezumab with rimegepant with respect to onset of 50% sustained response	The initial month at which galcanezumab was superior to rimegepant in the proportion of patients meeting at least a 50% reduction in monthly migraine headache days that is sustained at all subsequent months through Month 3
To assess other endpoints of interest	
To compare galcanezumab with rimegepant with respect to change in use of acute headache treatment	The overall mean change from baseline in the number of monthly days with acute headache medication use during the 3-month double-blind treatment period
To compare galcanezumab with rimegepant with respect to monthly moderate to severe migraine headache days	The overall mean change from baseline in the number of monthly moderate to severe migraine headache days across the 3-month double-blind treatment period
To compare galcanezumab with rimegepant with respect to 50% response rate in moderate to severe migraine headache days	Percentage of participants with $\geq 50\%$ reduction from baseline in moderate to severe monthly migraine headache days across the 3-month double-blind treatment period

* Weekly onset was defined as the initial week at which galcanezumab was superior to rimegepant and maintained superiority at all subsequent weeks during that month..

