18.4. EXPLORATORY EFFICACY

The exploratory efficacy analyses will be performed for the ITT. Table K summarizes all the planned secondary efficacy analyses.

Document: CCI

Author: PPD

Version Number: 3.0

Version Date: 19May2023

CCI

Table K: Exploratory Efficacy Variables and Analysis Methods

Efficacy Variables	Analysis
Change from baseline in the Patient Global Impression of Severity (PGI-S) at Month 3	ANCOVA
Change from baseline in the number of monthly moderate to severe headache days across the 3-month double-blind treatment period	MMRM
Change from baseline in the Monthly Total Pain Burden across the 3-month double-blind treatment period	MMRM
50% response rate: 
 Percentage of participants with $\geq 50\%$ reduction from baseline in monthly migraine headache days at Month 3, Month 2, and Month 1 Percentage of participants with $\geq 50\%$ reduction in Weekly migraine headache days at weeks 4, 3, 2, 1 in the months that galcanezumab was superior to rimegepant The initial month at which galcanezumab was superior to rimegepant in the proportion of patients meeting at least a 50% reduction in monthly migraine headache days that is sustained at all subsequent months through Month 3 Percentage of participants with $\geq 50\%$ reduction from baseline in moderate to severe monthly migraine headache days across the 3-month double-blind treatment period 	GLIMMIX
Change from baseline in the number of weekly migraine headache days in the months that galcanezumab was superior to rimegepant	MMRM
Change from baseline in the number of monthly days with acute headache medication use during the 3-month double-blind treatment phase	MMRM
Change from baseline in the number of monthly moderate to severe migraine headache days across the 3-month double-blind treatment period	MMRM

Abbreviations: ANCOVA = analysis of covariance; GLIMMIX = Generalized linear mixed model (for binary variables); MMRM = Mixed models repeated measures.

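### The exploratory weekly onset endpoints are estimated only in months where galcanezumab has already proved superior, which biases the reported weekly differences towards it

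*SAP*

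**What the plan says.** SAP 2.3, Table D, adds exploratory onset objectives that are not in the protocol (SAP 3.3 acknowledges the addition). The weekly headache-day objective is a plain two-drug comparison: "To compare galcanezumab with rimegepant with respect to weekly migraine headache days by Week 4, Week 3, Week 2, and Week 1". The endpoint set against it is narrower: "Mean change from baseline in the number of weekly migraine headache days in the months that galcanezumab was superior to rimegepant". The weekly 50% response endpoint carries the same limit, "in the months that galcanezumab was superior to rimegepant". The restriction reappears in Table K (SAP 18.4), for example "Change from baseline in the number of weekly migraine headache days in the months that galcanezumab was superior to rimegepant", and in SAP 18.4.1, so it is not a slip in one table.

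The Table D footnote defines onset in one direction: "Weekly onset was defined as the initial week at which galcanezumab was superior to rimegepant and maintained superiority at all subsequent weeks during that month". There is no matching definition for rimegepant, and no weekly analysis is listed for other months.

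Under the same onset heading, the monthly response endpoint has no such limit: "reduction from baseline in monthly migraine headache days at Month 3, Month 2, and Month 1". The key secondary changes in headache days at Months 1, 2 and 3 (Table A) are not restricted either.

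**The concern.** The objective and its endpoints do not match. The objective asks how the two drugs compare week by week. The endpoints answer that only after the month has come out in favour of one of them. The weekly counts are parts of the monthly count, so this is selection on the outcome being estimated, and estimates that survive such a filter are too large on average.

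The filter also works one way. A month with no difference, or with rimegepant ahead, has no planned weekly result, so an early rimegepant advantage would usually go unreported. SAP 18.2.4 itself recognises that expectations about onset may differ between these two regimens. At stake is the credibility of a descriptive onset result in a head-to-head trial meant to inform prescribers. No confirmatory claim is at stake.

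**Working it through.** **Inputs.** SAP 18.1.2: in each month, Weeks 1 to 3 are 7 days each and Week 4 is the remainder (30 − 21 = 9 days in a 30-day month). SAP 6.5: default two-sided 5% level, hence z > 1.96 in galcanezumab's direction. The plan gives no figure for the weekly endpoints. Its only power statement (SAP 3.1.1: about 575 participants, a 12-point difference, more than 85%) is for the primary endpoint, with the detail held in a separate document, so single-month power is unknown and is shown as a range.

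**Assumption.** A month is superior if z > 1.96 on monthly migraine headache days. The SAP names neither the endpoint (days or 50% response) nor the test, and does not say whether the month must also be reached in the testing hierarchy.

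**Step 1: weeks and month.** With a complete diary, the monthly difference equals the sum of the four weekly differences. Whatever proportion selection adds to the month, it adds to that sum, and so to the weekly differences on average. Missing diary days and separate model fits make this approximate. Weekly 50% response is a threshold applied week by week and does not add up to monthly response, so there the result is only a guide.

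**Step 2: size.** For a true monthly z of d,

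E[Z | Z > 1.96] = d + φ(1.96 − d) / (1 − Φ(1.96 − d)).

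| True z | Chance the month is selected | Mean z if selected | Overstatement |
|---|---|---|---|
| 1.96 | 50% | 2.76 | 2.76/1.96 − 1 = 41% |
| 2.5 | Φ(0.54) = 71% | 2.99 | 2.99/2.5 − 1 = 20% |
| 3.0 | Φ(1.04) = 85% | 3.27 | 3.27/3.0 − 1 = 9% |

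**Step 3: a single week.** Take four equally variable weekly estimates with common correlation ρ (assumed 0.2 to 0.6). The correlation of a week with its month is √((1 + 3ρ)/4): 0.63, 0.74 and 0.84 at ρ = 0.2, 0.4 and 0.6.
- Monthly z of 2, ρ = 0.4, equal effects: each week's true z is 0.74 × 2 = 1.48. The selected mean is 0.74 × 2.77 = 2.06.
- No true difference: E[Z | Z > 1.96] = φ(1.96)/0.025 = 2.34, so the selected weekly estimates average 1.48 to 1.96 standard errors towards galcanezumab instead of 0.

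A simulation of 1,000,000 runs per scenario gave the same values.

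**Step 4: direction.** Suppose rimegepant is truly ahead by 3 weekly standard errors in Week 1 and the drugs are equal afterwards. The true monthly z is −3/√(4 + 12ρ), that is −1.19 at ρ = 0.2 and −0.90 at ρ = 0.6. The month is then selected with probability 0.08% to 0.21%, although Week 1 alone would be significant for rimegepant with probability Φ(3 − 1.96) = 85%.

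**Step 5: false positives.** With no true difference, Week 4 would be called superior in 2.5% of unselected months. Requiring the month as well lowers the joint rate to 0.7% to 1.2%. The restriction therefore biases estimates but does not inflate unconditional type I error.

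**The case against.** The strongest reply is that these are prespecified, exploratory, unadjusted endpoints. The hypotheses in SAP 6.5 are themselves directional, and looking at weeks only after the month succeeds is a step-down that limits false onset claims. All of that stands, and Step 5 supports the last part. It justifies a condition on *declaring* galcanezumab onset. It does not justify withholding the weekly *estimates* when the month goes otherwise. The output templates cited in SAP 8 were not available and may show more weeks than the text requires, but the text as written does not call for them.

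A reader might infer more than the documents support:

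- *That the trial cannot compare onset.* It can, by month: headache-day change and 50% response at Months 1, 2 and 3 are unrestricted, so a Month 1 advantage for rimegepant would be visible. Only the weekly resolution is lost.
- *That an unfavourable Month 1 removes all weekly results.* Months 2 and 3 would still be analysed by week if galcanezumab were superior there.
- *That every weekly estimate must favour galcanezumab.* With rimegepant 3 standard errors ahead in Week 1 and galcanezumab 3 ahead in Weeks 2 to 4, the month was selected and Week 1 was significant for rimegepant in 29% to 52% of simulated runs. The one-way limit is exact only for the defined onset result.
- *That the overstatement is typically very large.* At a true z of 1.0 the formula gives 2.49, or 149%, but that month has only a 17% chance of selection. Nothing in the documents points to that case over the 9% case.

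**Conclusion.** The point holds as a minor one. Followed as written, the plan produces weekly onset estimates selected on their own outcome and biased towards galcanezumab, and plans none for months with no difference or with rimegepant ahead.

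The overstatement is about 9% where the month has about 85% power, 20% at 71% and 41% at 50%, growing as power falls. These figures rest on reading superior as z > 1.96 on monthly headache days. They apply to weekly headache days on average and only approximately to weekly 50% response. The single-week figures also rest on the assumed correlations. The undefined term is a defect in its own right, because it leaves the analyst to choose which months qualify.

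The monthly onset comparisons, the primary and key secondary inference and the unconditional type I error are not affected.

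**What to change.** In Table D, Table K and SAP 18.4.1, remove the restriction. Estimate the weekly differences in headache days and in 50% response, with 95% CIs, for every week of Months 1 to 3 in all ITT participants, whatever the monthly result. Reword the Table D footnote so that onset is assigned to whichever drug is superior. If a monthly condition is kept for declaring galcanezumab onset, use it for that label only and not to decide which weekly estimates are produced. State the monthly endpoint and test that define superior, and whether the testing hierarchy applies.

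The daily diary data are already collected, so the cost is a few more exploratory tables. No alpha is involved.

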2.4. ESTIMANDS

The primary estimand is the difference in effect for galcanezumab compared to rimegepant in participants with episodic migraine on the overall mean monthly 50% response rate (defined as participants with at least a 50% reduction from baseline in the frequency of migraine headache days) across the 3-month double-blind period (See estimand in Table E below).

All available monthly migraine headache data will contribute to analysis as long as baseline monthly migraine headache day values are available. Any migraine headache day after study

Document: **CCI**

Author: **PPD**

Version Number:

3.0

Version Date:

19May2023

CCI

intervention discontinuation but within the double-blind period will still be used within the analysis as estimated from the model using the GLIMMIX procedure.

For all secondary endpoints, a similar estimand to the one used for the primary analysis will be employed. That is, the estimand of interest will be based on overall mean monthly estimates across/within the double-blind period and will be based on all available data during that period (even if collected after study intervention discontinuation). Additionally, baseline values must also be available.

The primary and the key secondary estimands are described in Table E:

Table E: Estimands

Objective	Estimands
Primary	
To assess whether galcanezumab is superior to rimegepant in the prevention of migraine in participants with episodic migraine	
Treatment condition: Galcanezumab injections of 120 mg SC or rimegepant 75 mg ODT regardless of initiation of new preventive migraine medication, regardless the use of acute medication to treat a migraine headache and regardless of discontinuing treatment due to any reason (treatment policy strategy)
 
Population: Participants who meet IHS-ICHD-3 (2018) criteria for a diagnosis of migraine with or without aura with an episodic frequency of 4 to 14 migraine headache days per month and fulfils the inclusion and exclusion criteria of the study.
 
Variable (endpoint): The percentage of participants with $\geq 50\%$ reduction from baseline in monthly migraine headache days across the 3-month double-blind treatment period
 
Remaining intercurrent event handling: NA
 
Summary measure: Difference of the overall mean monthly 50% response rate across the 3-month double-blind treatment period between treatment

Document: **CCI**

Author: **PPD**

Version Number:

3.0

Version Date:

19May2023

CCI

Objective	Estimands
	groups
Primary Sensitivity 1	
To assess whether galcanezumab is superior to rimegepant in the prevention of migraine in participants with episodic migraine	
Treatment condition: Galcanezumab injections of 120 mg SC or rimegepant 75 mg ODT regardless the use of acute medication to treat a migraine headache and regardless of discontinuing treatment due to any reason (treatment policy strategy)
 
Population: Participants who meet IHS-ICHD-3 (2018) criteria for a diagnosis of migraine with or without aura with an episodic frequency of 4 to 14 migraine headache days per month and fulfils the inclusion and exclusion criteria of the study.
 
Variable (endpoint): The percentage of participants with $\geq 50\%$ reduction from baseline in monthly migraine headache days across the 3-month double-blind treatment period
 
Remaining intercurrent event handling: The data after whichever of the following is sooner: the date of the last injection+30 days or the date of the last oral administration +1 day, will be discarded.
 
Summary measure: Difference of the overall mean monthly 50% response rate across the 3-month double-blind treatment period between treatment groups

Primary Sensitivity 2	
To assess whether galcanezumab is superior to rimegepant in the prevention of migraine in participants	
Treatment condition: Galcanezumab injections of 120 mg SC or rimegepant 75 mg ODT regardless of initiation of new preventive migraine medication, regardless the use of acute medication to treat an acute migraine attack and regardless of discontinuing treatment due to any reason (treatment policy strategy)

Document: CCI

Author: PPD

Version Number: 3.0

Version Date: 19May2023

Objective	Estimands
with episodic migraine	
Population: Participants who meet IHS-ICHD-3 (2018) criteria for a diagnosis of migraine with or without aura with an episodic frequency of 4 to 14 migraine headache days per month and fulfils the inclusion and exclusion criteria of the study.

	
Variable (endpoint): The percentage of participants with $\geq 50\%$ reduction from baseline in monthly migraine headache days across the 3-month double-blind treatment period

	
Remaining intercurrent event handling: The participants that withdraw for lack of efficacy or tolerability, or participants that initiate a new preventive treatment will be considered as non-responders (composite strategy)

	
Summary measure: Difference of the overall mean monthly 50% response rate across the 3-month double-blind treatment period between treatment groups

Primary Sensitivity 3	
To assess whether galcanezumab is superior to rimegepant in the prevention of migraine in participants with episodic migraine	
Treatment condition: Galcanezumab injections of 120 mg SC or rimegepant 75 mg ODT regardless of initiation of new preventive migraine medication, regardless the use of acute medication to treat an acute migraine attack and regardless of discontinuing treatment due to any reason (treatment policy strategy)

	
Population: Participants who meet IHS-ICHD-3 (2018) criteria for a diagnosis of migraine with or without aura with an episodic frequency of 4 to 14 migraine headache days per month and fulfils the inclusion and exclusion criteria of the study. (This population will not include participants that take acute medication and do not meet the migraine headache criteria at baseline.)

	
Variable (endpoint):

Document: **CCI**Author: **PPD**

Version Number:

3.0

Version Date:

19May2023

Objective	Estimands
	
The percentage of participants with $\geq 50\%$ reduction from baseline in monthly migraine headache days across the 3-month double-blind treatment period

	
Remaining intercurrent event handling: A migraine headache day will be considered when the participant takes acute medication regardless if the headache does not meet the criteria of migraine. This analysis will consider if a participant uses an acute medication (triptans or ergot derivatives) – as reported in the CM_AHM eCRF, regardless of whether a headache was reported. Subjects using a Triptan and/or ergot derivative will be identified by medical review of the eCRF.

	
Summary measure: Difference of the overall mean monthly 50% response rate across the 3-month double-blind period between treatment groups

Primary Sensitivity 4	
To compare galcanezumab with rimegepant with respect to monthly migraine headache days	
Treatment condition: Galcanezumab injections of 120 mg SC or rimegepant 75 mg ODT, regardless of initiation of new preventive migraine medication, regardless the use of acute medication to treat an acute migraine attack and regardless of discontinuing treatment due to any reason (treatment policy strategy)
 
Population: Participants who meet IHS-ICHD-3 (2018) criteria for a diagnosis of migraine with or without aura with an episodic frequency of 4 to 14 migraine headache days per month and fulfills the inclusion and exclusion criteria of the study.
 
Variable (endpoint): The overall mean change from baseline in the number of monthly migraine headache days across the 3-month double-blind treatment period
 
Remaining intercurrent event handling: To assess the robustness of the primary analysis conclusions to

Document: CCI

Author: PPD

Version Number: 3.0

Version Date: 19May2023

Objective	Estimands
	
deviations from missing at random (MAR) assumption, this analysis will vary the assumptions of missing data for the primary analysis in a systematic way.

	
Summary measure: Difference of the overall mean change from baseline in the number of monthly migraine headache days across the 3-month double-blind treatment period

Key Secondary	
To compare galcanezumab with rimegepant with respect to monthly migraine headache days	
Treatment condition: Galcanezumab injections of 120 mg SC or rimegepant 75 mg ODT, regardless of initiation of new preventive migraine medication, regardless the use of acute medication to treat an acute migraine attack and regardless of discontinuing treatment due to any reason (treatment policy strategy)

	
Population: Participants who meet IHS-ICHD-3 (2018) criteria for a diagnosis of migraine with or without aura with an episodic frequency of 4 to 14 migraine headache days per month and fulfils the inclusion and exclusion criteria of the study.

	
Variable (endpoint): The overall mean change from baseline in the number of monthly migraine headache days across the 3-month double-blind treatment period

	
Remaining intercurrent event handling: NA

	
Summary measure: Difference of the overall mean change from baseline in the number of monthly migraine headache days across the 3-month double-blind treatment period

To compare galcanezumab	
Treatment condition: Galcanezumab injections of 120 mg SC or rimegepant 75 mg ODT,

Document: **CCI**Author: **PPD**Version Number: **3.0**Version Date: **19May2023**

Objective	Estimands
with rimegepant with respect to 75% response rate	
regardless of initiation of new preventive migraine medication, regardless the use of acute medication to treat an acute migraine attack and regardless of discontinuing treatment due to any reason (treatment policy strategy)

	
Population: Participants who meet IHS-ICHD-3 (2018) criteria for a diagnosis of migraine with or without aura with an episodic frequency of 4 to 14 migraine headache days per month and fulfills the inclusion and exclusion criteria of the study.

	
Variable (endpoint): The percentage of participants with $\geq 75\%$ reduction from baseline in monthly migraine headache days across the 3-month double-blind treatment period

	
Remaining intercurrent event handling: NA

	
Summary measure:

	
Difference of the overall mean monthly 75% response rate across the 3-month double-blind period between treatment groups

To compare galcanezumab with rimegepant with respect to monthly migraine headache days at each month	
Treatment condition: Galcanezumab injections of 120 mg SC or rimegepant 75 mg ODT, regardless of initiation of new preventive migraine medication, regardless the use of acute medication to treat an acute migraine attack and regardless of discontinuing treatment due to any reason (treatment policy strategy)

	
Population: Participants who meet IHS-ICHD-3 (2018) criteria for a diagnosis of migraine with or without aura with an episodic frequency of 4 to 14 migraine headache days per month and fulfills the inclusion and exclusion criteria of the study.

	
Variable (endpoint): The mean change from baseline in the number of monthly migraine headache days at:

Document: CCI

Author: PPD

Version Number: 3.0

Version Date: 19May2023

Objective	Estimands
	
 o Month 3 o Month 2 o Month 1
	
Remaining intercurrent event handling: NA

	
Summary measure: Difference of the mean change from baseline in the number of monthly migraine headache days at:
 
 o Month 3 o Month 2 o Month 1

To compare galcanezumab with rimegepant with respect to migraine headache days with acute (abortive) migraine treatment
	
Treatment condition: Galcanezumab injections of 120 mg SC or rimegepant 75 mg ODT, regardless of initiation of new preventive migraine medication, regardless the use of acute medication to treat an acute migraine attack and regardless of discontinuing treatment due to any reason (treatment policy strategy). Medication use will be based on response to question 12 of the diary.

	
Population: Participants who meet IHS-ICHD-3 (2018) criteria for a diagnosis of migraine with or without aura with an episodic frequency of 4 to 14 migraine headache days per month and fulfils the inclusion and exclusion criteria of the study.

	
Variable (endpoint): The overall mean change from baseline in the number of monthly migraine headache days requiring medication for the acute treatment of migraine or headache across the 3-month double-blind treatment period

	
Remaining intercurrent event handling: NA

	
Summary measure: Difference of the overall mean change from baseline in the number

Document: CCI

Author: PPD

Version Number: 3.0

Version Date: 19May2023

Objective	Estimands
	of monthly migraine headache days requiring medication for the acute treatment of migraine or headache across the 3-month double-blind treatment period
To compare galcanezumab with rimegepant with respect to change in functioning	
Treatment condition: Galcanezumab injections of 120 mg SC or rimegepant 75 mg ODT, regardless of initiation of new preventive migraine medication, regardless the use of acute medication to treat an acute migraine attack and regardless of discontinuing treatment due to any reason (treatment policy strategy)
 
Population: Participants who meet IHS-ICHD-3 (2018) criteria for a diagnosis of migraine with or without aura with an episodic frequency of 4 to 14 migraine headache days per month and fulfils the inclusion and exclusion criteria of the study.
 
Variable (endpoint): The mean change from baseline in the Role Function-Restrictive (RF-R) domain score of the Migraine-Specific Quality of Life Questionnaire version 2.1 (MSQ v2.1) at Month 3
 
Remaining intercurrent event handling: NA
 
Summary measure: Difference of the mean change from baseline in the Role Function-Restrictive (RF-R) domain score of the Migraine-Specific Quality of Life Questionnaire version 2.1 (MSQ v2.1) at Month 3

To compare galcanezumab with rimegepant with respect to 100% response rate	
Treatment condition: Galcanezumab injections of 120 mg SC or rimegepant 75 mg ODT, regardless of initiation of new preventive migraine medication, regardless the use of acute medication to treat an acute migraine attack and regardless of discontinuing treatment due to any reason (treatment policy strategy)
 
Population: Participants who meet IHS-ICHD-3 (2018) criteria for a diagnosis

Document: CCI

Author: PPD

Version Number: 3.0

Version Date: 19May2023

Objective	Estimands
	of migraine with or without aura with an episodic frequency of 4 to 14 migraine headache days per month and fulfils the inclusion and exclusion criteria of the study.
	Variable (endpoint): The percentage of participants with 100% reduction from baseline in monthly migraine headache days across the 3-month double-blind treatment period
	Remaining intercurrent event handling: NA
	Summary measure: Difference of the overall mean monthly 100% response rate across the 3-month double-blind period between treatment groups

